#### 11.1.3 Methods for evaluation of measurable disease

All measurements should be taken and recorded in metric notation using a ruler or calipers. All baseline evaluations should be performed as closely as possible to the beginning of treatment and never more than 4 weeks before the beginning of the treatment.

The same method of assessment and the same technique should be used to characterize each identified and reported lesion at baseline and during follow-up.

Imaging-based evaluation is preferred to evaluation by clinical examination unless the lesion(s) being followed cannot be imaged but are assessable by clinical exam.

*Clinical lesions*: Clinical lesions will only be considered measurable when they are superficial (e.g., skin nodules and palpable lymph nodes). In the case of skin lesions, documentation by color photography, including a ruler to estimate the size of the lesion, is recommended.

*Chest x-ray*: Lesions on chest x-ray are acceptable as measurable lesions when they are clearly defined and surrounded by aerated lung. However, CT is preferable.

*Conventional CT and MRI*: This guideline has defined measurability of lesions on CT scan based on the assumption that CT slice thickness is 5 mm or less. If CT scans have slice thickness greater than 5 mm, the minimum size for a measurable lesion should be twice the slice thickness. MRI is also acceptable in certain situations (e.g. for body scans).

Use of MRI remains a complex issue. MRI has excellent contrast, spatial, and temporal resolution; however, there are many image acquisition variables involved in MRI, which greatly impact image quality, lesion conspicuity, and measurement. Furthermore, the availability of MRI is variable globally. As with CT, if an MRI is performed, the technical specifications of the scanning sequences used should be optimized for the evaluation of the type and site of disease. Furthermore, as with CT, the modality used at follow-up should be the same as was used at baseline and the lesions should be measured/assessed on the same pulse sequence. It is beyond the scope of the RECIST guidelines to prescribe specific MRI pulse sequence parameters for all scanners, body parts, and diseases. Ideally, the same type of scanner should be used and the image acquisition protocol should be followed as closely as possible to prior scans. Body scans should be performed with breath-hold scanning techniques, if possible.

*PET-CT*: At present, the low dose or attenuation correction CT portion of a combined PET-CT is not always of optimal diagnostic CT quality for use with RECIST measurements. However, if the site can document that the CT performed as part of a PET-CT is of identical diagnostic quality to a diagnostic CT (with IV and oral contrast), then the CT portion of the PET-CT can be used for RECIST measurements and can be used interchangeably with conventional CT in accurately measuring cancer lesions over time. Note, however, that the PET portion of the CT introduces additional data, which may bias an investigator if it is not routinely or serially performed.

*Ultrasound*: Ultrasound is not useful in assessment of lesion size and should not be used as a method of measurement. Ultrasound examinations cannot be reproduced in their entirety for independent review at a later date and, because they are operator dependent, it cannot be guaranteed that the same technique and measurements will be taken from one assessment to the next. If new lesions are identified by ultrasound in the course of the study, confirmation by CT or MRI is

advised. If there is concern about radiation exposure at CT, MRI may be used instead of CT in selected instances.

Endoscopy, laparoscopy: The utilization of these techniques for objective tumor evaluation is not advised. However, such techniques may be useful to confirm complete pathological response when biopsies are obtained or to determine relapse in trials where recurrence following complete response (CR) or surgical resection is an endpoint.

Tumor markers: Tumor markers alone cannot be used to assess response. If markers are initially above the upper normal limit, they must normalize for a participant to be considered in complete clinical response. Specific guidelines for both CA-125 response (in recurrent ovarian cancer) and PSA response (in recurrent prostate cancer) have been published [JNCI 96:487-488, 2004; J Clin Oncol 17, 3461-3467, 1999; J Clin Oncol 26:1148-1159, 2008]. In addition, the Gynecologic Cancer Intergroup has developed CA-125 progression criteria, which are to be integrated with objective tumor assessment for use in first-line trials in ovarian cancer [JNCI 92:1534-1535, 2000].

Cytology, histology: These techniques can be used to differentiate between partial responses (PR) and complete responses (CR) in rare cases (e.g., residual lesions in tumor types, such as germ cell tumors, where known residual benign tumors can remain).

The cytological confirmation of the neoplastic origin of any effusion that appears or worsens during treatment when the measurable tumor has met criteria for response or stable disease is mandatory to differentiate between response or stable disease (an effusion may be a side effect of the treatment) and progressive disease.

FDG-PET: While FDG-PET response assessments need additional study, it is sometimes reasonable to incorporate the use of FDG-PET scanning to complement CT scanning in assessment of progression (particularly possible 'new' disease). New lesions on the basis of FDG-PET imaging can be identified according to the following algorithm:

- a. Negative FDG-PET at baseline, with a positive FDG-PET at follow-up is a sign of PD based on a new lesion. **However, as this may not necessarily represent a new tumor lesion for individuals with ongoing HIV replication, new lesions on FDG-PET MUST be confirmed by CT scan to document progressive disease.**
- b. No FDG-PET at baseline and a positive FDG-PET at follow-up: If the positive FDG-PET at follow-up corresponds to a new site of disease confirmed by CT, this is PD. If the positive FDG-PET at follow-up is not confirmed as a new site of disease on CT, additional follow-up CT scans are needed to determine if there is truly progression occurring at that site (if so, the date of PD will be the date of the initial abnormal FDG-PET scan). If the positive FDG-PET at follow-up corresponds to a pre-existing site of disease on CT that is not progressing on the basis of the anatomic images, this is not PD.

- c. FDG-PET may be used to upgrade a response to a CR in a manner similar to a biopsy in cases where a residual radiographic abnormality is thought to represent fibrosis or scarring. The use of FDG-PET in this circumstance should be prospectively described in the protocol and supported by disease-specific medical literature for the indication. However, it must be acknowledged that both approaches may lead to false positive CR due to limitations of FDG-PET and biopsy resolution/sensitivity.

**Note:** A ‘positive’ FDG-PET scan lesion means one which is FDG avid with an uptake greater than twice that of the surrounding tissue on the attenuation corrected image.

#### 11.1.4 Response criteria

##### 11.1.4.1 Evaluation of target lesions

Complete response (CR): Disappearance of all target lesions. Any pathological lymph nodes (whether target or non-target) must have reduction in short axis to <10 mm.

Partial response (PR): At least a 30% decrease in the sum of the diameters of target lesions, taking as reference the baseline sum diameters.

Progressive disease (PD): At least a 20% increase in the sum of the diameters of target lesions, taking as reference the smallest sum on study (this includes the baseline sum if that is the smallest on study). In addition to the relative increase of 20%, the sum must also demonstrate an absolute increase of at least 5 mm. (Note: the appearance of one or more new lesions is also considered progressions).

Stable disease (SD): Neither sufficient shrinkage to qualify for PR nor sufficient increase to qualify for PD, taking as reference the smallest sum diameters while on study.

##### 11.1.4.2 Evaluation of non-target lesions

Complete response (CR): Disappearance of all non-target lesions and normalization of tumor marker level. All lymph nodes must be non-pathological in size (<10 mm short axis).

Note: If tumor markers are initially above the upper normal limit, they must normalize for a participant to be considered in complete clinical response.

Non-CR/Non-PD: Persistence of one or more non-target lesion(s) and/or maintenance of tumor marker level above the normal limits.

Progressive disease (PD): Appearance of one or more new lesions and/or *unequivocal progression* of existing non-target lesions. *Unequivocal progression* should not normally trump target lesion status. It must be representative of overall disease status change, not a single lesion increase.

Although a clear progression of “non-target” lesions only is exceptional, the opinion of the treating physician should prevail in such circumstances, and the progression status should be confirmed at a later time by the review panel (or Principal Investigator).

#### 11.1.4.3 Evaluation of best overall response

The best overall response is the best response recorded from the start of the treatment until disease progression/recurrence (taking as reference for progressive disease the smallest measurements recorded since the treatment started). The participant's best response assignment will depend on the achievement of both measurement and confirmation criteria.

#### For Participants with Measurable Disease (*i.e.*, Target Disease)

Target Lesions	Non-Target Lesions	New Lesions	Overall Response	Best Overall Response when Confirmation is Required*	
CR	CR	No	CR	$\geq 4$ wks. Confirmation**	
CR	Non-CR/Non-PD	No	PR	$\geq 4$ wks. Confirmation**	
CR	Not evaluated	No	PR		
PR	Non-CR/Non-PD/not evaluated	No	PR		
SD	Non-CR/Non-PD/not evaluated	No	SD	Documented at least once $\geq 4$ wks. from baseline**	
PD	Any	Yes or No	PD	no prior SD, PR or CR	
Any	PD***	Yes or No	PD		
Any	Any	Yes	PD		
See RECIST 1.1 manuscript for further details on what is evidence of a new lesion.					
**Only for non-randomized trials with response as primary endpoint.					
***In exceptional circumstances, unequivocal progression in non-target lesions may be accepted as disease progression.					
Note: Participants with a global deterioration of health status requiring discontinuation of treatment without objective evidence of disease progression at that time should be reported as “ symptomatic deterioration .” Every effort should be made to document the objective progression even after discontinuation of treatment.					

### For Participants with Non-Measurable Disease (i.e., Non-Target Disease)

Non-Target Lesions	New Lesions	Overall Response
CR	No	CR
Non-CR/non-PD	No	Non-CR/non-PD*
Not all evaluated	No	not evaluated
Unequivocal PD	Yes or No	PD
Any	Yes	PD

*\*Non-CR/non-PD* is preferred over *'stable disease'* for non-target disease since SD is increasingly used as an endpoint for assessment of efficacy in some trials so to assign this category when no lesions can be measured is not advised

#### 11.1.5 Duration of response

*Duration of overall response:* The duration of overall response is measured from the time measurement criteria are met for CR or PR (whichever is first recorded) until the first date that recurrent or progressive disease is objectively documented (taking as reference for progressive disease the smallest measurements recorded since the treatment started).

The duration of overall CR is measured from the time measurement criteria are first met for CR until the first date that progressive disease is objectively documented.

*Duration of stable disease:* Stable disease is measured from the start of the treatment until the criteria for progression are met, taking as reference the smallest measurements recorded since the treatment started, including the baseline measurements.

### 11.2 Evaluation of Response for Participants with Kaposi Sarcoma

11.2.1 Complete response (CR) is defined as the absence of any detectable residual disease, including tumor-associated edema, persisting for at least 4 weeks. For participants in whom pigmented (brown or tan) macular skin lesions persist after apparent complete response, biopsy of at least one representative lesion is required in order to document the absence of malignant cells. Participants without visceral disease are not required to undergo radiographic measurements. In participants known to have had visceral disease, an assessment at restaging with appropriate endoscopic or radiographic procedures should be made.

11.2.2 Partial response (PR) is defined as no new lesions (skin or oral), or new visceral sites of involvement (or the appearance or worsening of tumor-associated edema or effusions); AND

- A 50% or greater decrease in the number of all previously existing lesions lasting for at least 4 weeks; OR
- Complete flattening of at least 50% of all previously raised lesions (i.e., 50% of all previously nodular or plaque-like lesion become macules); OR

- A 50% decrease in the sum of the products of the largest perpendicular diameters of the marker lesions

**Note:** Participants with residual tumor-associated edema or effusion who otherwise meet the criteria for complete response will be classified as having a partial response.

11.2.3 Stable disease (SD) is defined as any response not meeting the criteria for CR, PR, or progressive disease.

11.2.4 Progressive disease (PD) is defined as follows:

*For participants with  $\leq 50$  cutaneous lesions*

1.  $> 25\%$  increase in the sum of perpendicular diameters of the indicator lesions, OR
2.  $\geq 25\%$  increase in the total lesion count, or a minimum of 5 new lesions, whichever is greater, OR
3.  $\geq 25\%$  increase in the number of raised lesions (minimum of 5 new raised lesions if there are very few raised lesions, for example  $\leq 8$ ), whichever is greater.

**Note:** There are body sites where disease is particularly difficult to evaluate, and a few new lesions may be counted in spite of the fact that a participant is not actually progressing. For example, lesions of the foot, particularly those which are flat, are difficult to evaluate because their intensity may be variable based on how much edema is present, how much the person walked the day before, how long their feet have been in a dependent position prior to the physical exam, etc.

*For participants with  $> 50$  cutaneous lesions*

1.  $\geq 25\%$  increase in the sum of the perpendicular diameters of the indicator lesions, OR
2.  $\geq 25\%$  increase in the total number of lesions in the prospectively defined anatomic sites containing representative numbers of lesions, OR
3. A total of 5 new lesions in anatomic sites which were previously documented as having no evidence of cutaneous disease on the whole body diagram, OR
4.  $\geq 25\%$  increase in the number of raised lesions (minimum of 5 raised lesions if there are very few raised lesions, for example  $<8$ ) whichever is greater. Photographic documentation of “gross” or significant progression, particularly in areas that were not being followed, will be of particular value.

In order to classify a response as PR, the participant must have at least a PR in either the cutaneous or noncutaneous sites of disease, and no evidence of progression as defined in the above criteria. In order to classify a response as a CR, the participant must have a CR in both the cutaneous (if applicable) and noncutaneous (if applicable) sites of disease and no evidence of progression as defined by the above criteria.

*Noncutaneous Progression*

Progressive disease includes new visceral sites of involvement or progression of visceral disease or the development of new or increasing tumor-associated edema or effusion lasting at least 1 week, which interferes with the participant's normal activities. Progressive visceral disease, for measurable and evaluable disease, should be analogous to non-KS response criteria.

- 11.2.5 Recurrent disease is defined as the appearance of tumor following documentation of a complete remission.
- 11.2.6 Time to response is defined as time from the first dose of chemotherapy until documentation of first response.
- 11.2.7 Time to progression is defined as time from initiation of chemotherapy to documentation of first progression.
- 11.2.8 Response duration is defined as the time from first documentation of response to documentation of first progression.

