## 11.0 MEASUREMENT OF EFFECT

Although response is not the primary endpoint of this trial, participants with measurable disease will be assessed by standard criteria. For the purposes of this study, participants should be re-evaluated every  $8 \pm 1$  weeks. In addition to a baseline scan, confirmatory scans will also be obtained at least 4 weeks following initial documentation of an objective response. **Participants with solid tumors other than Kaposi sarcoma will be followed for response according to [Section 11.1](#), and participants with Kaposi sarcoma will be followed for response according to [Section 11.2](#).**

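### Kaposi sarcoma partial response carries a four-week duration on only one of its three routes, and the size rules for response and progression use different measures with no stated reference for progression

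*Combined protocol and SAP*

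**What the plan says.** **Response.** Section 11.2.1 defines KS complete response as "the absence of any detectable residual disease, including tumor-associated edema, persisting for at least 4 weeks". Section 11.2.2 then sets a stem for PR (no new skin, oral or visceral involvement, and no new or worsening edema or effusion) followed by three routes joined by OR:

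- Lesion count: "A 50% or greater decrease in the number of all previously existing lesions lasting for at least 4 weeks; OR"
- Flattening: "Complete flattening of at least 50% of all previously raised lesions"
- Size: "A 50% decrease in the sum of the products of the largest perpendicular diameters of the marker lesions"

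Only the first contains a duration. Section 11.2.8 starts response duration when response is first documented.

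**Confirmation.** Section 11.0, before it sends KS participants to 11.2, says that "confirmatory scans will also be obtained at least 4 weeks following initial documentation of an objective response". Section 9.2.8 exempts cutaneous KS from CT, and 11.2.1 exempts participants without visceral disease from radiographic measurement. Section 9.2.9 schedules KS response assessment after every other cycle.

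**Progression by size (11.2.4).** With 50 or fewer lesions the rule is a rise of strictly more than 25%: "increase in the sum of perpendicular diameters of the indicator lesions, OR". With more than 50 lesions it is a rise of at least 25%: "increase in the sum of the perpendicular diameters of the indicator lesions, OR". Neither names the value from which the rise is measured.

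**Use.** Section 12.4 reports binomial response proportions with 95% confidence intervals for malignancies with at least 4 participants. Section 5.4 lists disease progression as a reason to end treatment.

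**The concern.** There are two separate defects in the endpoint definition.

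First, a participant whose raised lesions are flat at one visit and raised again at the next is a responder under the flattening route. The same fluctuation in lesion number would not count under the lesion-count route. The rate reported under 12.4 then mixes sustained and single-visit responses, and 11.2.8 starts a duration from the single-visit ones.

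Second, the size criteria do not form one system. Shrinkage is judged on an area-like scale and growth on a length scale, in lesions called marker in one place and indicator in the other. With no reference for growth, two assessors can classify identical measurements differently. Since progression ends treatment, this affects more than a summary table.

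**Working it through.** The plan states no figure that depends on the KS criteria, so there is nothing to reproduce. The check has four parts.

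**1. Where the duration applies**

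| Category or route | Section | Four weeks required? |
|---|---|---|
| Complete response | 11.2.1 | Yes |
| PR, lesion count | 11.2.2 | Yes |
| PR, flattening | 11.2.2 | Not stated |
| PR, sum of products | 11.2.2 | Not stated |

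Section 11.0 would fill the gap only if its reference to scans covered a skin examination. Section 11.2 does not repeat it for skin findings. With assessment every other 28-day cycle, the next scheduled KS assessment is 8 weeks later, so no four-week repeat lesion assessment is scheduled.

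**2. Putting the two size scales side by side**

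Assume every diameter changes by the same factor (shape unchanged):

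- Diameters +25%: products change by 1.25² − 1 = +56.25%.
- Products +25%: diameters change by √1.25 − 1 = +11.8%.
- Products −50% (the PR threshold): diameters change by √0.5 − 1 = −29.3%.

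The relation depends on which lesions grow. Take one 40×40 mm and one 10×10 mm lesion, with only the small one growing, to 22.5×22.5 mm:

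- Sum of diameters: 40+40+10+10 = 100, rising to 40+40+22.5+22.5 = 125, or +25%.
- Sum of products: 1600+100 = 1700, rising to 1600+506.25 = 2106.25, or +23.9%.

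Here the diameter rule is met while a 25% product rule would not be. The mismatch has no fixed direction.

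**3. The missing reference value**

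Take a participant who just reached PR by size, with shape unchanged. Diameters at the smallest point are √0.5 = 0.707 of baseline.

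- Regrowth to baseline size is 1/0.707 − 1 = +41% from the smallest value, which meets the 25% rule. From baseline it is 0%, which does not.
- If baseline is the reference, the rule is met only at 1.25/0.707 − 1 = +77% from the smallest value.

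The same lesions are therefore progressive under one reading and not under the other. For solid tumors, 11.1.4.1 names the smallest sum on study. Section 11.2.4 makes visceral KS analogous to the non-KS criteria but says nothing equivalent for skin lesions.

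**4. Effect of one transient response on the reported rate**

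No KS number is planned, so the sizes below are assumptions. The lowest is the reporting minimum in 12.4. Intervals are exact (Clopper-Pearson), also an assumption, since 12.4 does not name the type.

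| KS participants (assumed) | No response: rate (95% CI) | One response: rate (95% CI) |
|---|---|---|
| 4 | 0% (0 to 60.2%) | 25% (0.6 to 80.6%) |
| 6 | 0% (0 to 45.9%) | 16.7% (0.4 to 64.1%) |
| 8 | 0% (0 to 36.9%) | 12.5% (0.3 to 52.7%) |

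**The case against.** **The flattening route is not lax.** It requires complete flattening of at least half of the raised lesions, none of the new disease listed in the stem, and no evidence of progression. That is true, and false responses may be few. It still does not supply a duration.

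**Section 11.0 may already require confirmation.** If its sentence is read to cover skin findings, most of the first defect disappears. The word used is scans, however, and cutaneous KS needs none. The ambiguity is enough reason to settle it.

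**The protocol gives no evidence that flattening is transient.** A reader might use the remark in 11.2.4 that "their intensity may be variable based on how much edema is present". That remark concerns foot lesions, especially flat ones, and warns against counting false new lesions as progression. It does not show that raised lesions flatten temporarily, and the point here does not rest on it.

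**The size thresholds are not obviously unbalanced.** On the diameter scale with shape unchanged, KS response is a 29.3% fall and KS progression a 25% rise. The RECIST thresholds in 11.1.4.1 are a 30% fall and a 20% rise. This objection stands: different measures do not by themselves make progression too hard to reach.

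**The impact is small.** Response is not the primary endpoint, the rates are preliminary, and the intervals in the table overlap almost completely. This also stands and limits the weight of the point.

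**Conclusion.** The concern holds in a limited form. As written, two of the three KS PR routes need no persistence, while complete response and the third PR route need four weeks. Section 11.0 does not clearly repair this. The size criteria also use two measures, two inequalities and two lesion terms, and name no reference for cutaneous progression.

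A reader might go further and infer that size progression is called late, so that both defects favor the drug. The documents do not support that. Lateness can be measured only against a 25% rule on products, which the protocol never states for progression, and the mixed-lesion example reverses the direction. Progression can also be called on lesion count, raised lesions, new lesions or noncutaneous disease, so a late size call need not mean a late progression call. The diameter wording may simply be a drafting slip for products.

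The consequence is confined to a secondary, preliminary KS response rate, reported only if at least 4 KS participants enrol (one transient PR moves it by 25 points at an assumed 4 and 12.5 points at an assumed 8), and to consistency of KS progression calls. The percentages linking diameters and products assume unchanged lesion shape.

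**What to change.** **Response (11.2.2).** Move the four-week condition from the lesion-count route to the stem, so that it governs all three routes. Do the repeat lesion assessment at the day-1 physical examination of the next 28-day cycle, which Section 9.2 and Appendix I already schedule. Section 9.2 allows evaluations to move by 7 days either way, so two adjacent visits could be as close as 28 − 14 = 14 days; the text should say that the window may not shorten the interval below four weeks. Response that persists can still be dated from first documentation, as 11.2.8 has it.

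The cost is one extra lesion assessment per responder and possibly fewer KS PRs. No new visit is needed, but the lesion count and measurement are additional work, because 11.0 cannot be relied on as already requiring them.

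**Progression (11.2.4).** The sponsor should reconcile the size wording with 11.2.2: state one size measure for response and progression or justify two, name the reference value for the rise, use one inequality in both lesion-count groups, and use one term for the measured lesions. Because progression ends treatment under 5.4, the choice of measure and reference belongs to the sponsor, and none is proposed here. The cost is a wording amendment.
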